Safety Evaluation Criteria:	All local and systemic adverse events (AEs) observed by or reported to the Investigator throughout the study will be evaluated. The intensity, duration, and causal relationship to the investigational patch are to be rated for all AEs.
Statistical Methods:	Cumulative irritancy will be quantified for each subject/product by the mean and total cumulative irritancy score. This parameter will be tested pair wise for product differences using analysis of variance (subject, product).
Number of Study Centers:	Single center

Signature page

Product names: **CCP-020 (Diacerein 1%) Topical Ointment**
Vehicle

[figure not shown]
TKL Study number: **DS310717**

Sponsor protocol number: **CCP-020-102**

The signatures of the representatives on the following page constitute their approval of this protocol and provide the necessary assurances that this study will be conducted according to all stipulations stated in the protocol, including all statements as to confidentiality. It is also agreed that the study will not be initiated without the approval of an appropriate Institutional Review Board.

Approved by the following:

Sponsor

Signature page for the Principal Investigator

[figure not shown]
Product names: CCP-020 (Diacerein 1%) Topical Ointment

Vehicle

TKL Study number: DS310717

Sponsor protocol number: CCP-020-102

I have read this protocol and agree to conduct this study in accordance with all stipulations of the protocol and in accordance with the Declaration of Helsinki.

Investigators and study administrative structure

This figure consists of a 10x3 grid of horizontal bar charts. Each cell in the grid contains a black bar. The length of the bars varies, indicating data values. The bars are positioned at different heights within each cell, suggesting multiple data series or conditions per cell. The grid is defined by vertical and horizontal lines, creating a structure of 10 rows and 3 columns.

TABLE OF CONTENTS

Signature page.....	3
Signature page for the Principal Investigator.....	4
Investigators and study administrative structure.....	5
List of Abbreviations	9
1. INTRODUCTION	10
1.1. Background Information.....	10
1.2. Rationale for the Study	10
2. STUDY OBJECTIVES	12
3. INVESTIGATIONAL PLAN.....	13
3.1. Study Design.....	13
3.2. Discussion of Design	13
3.3. Study Population.....	13
3.3.1. Subject Population	13
3.3.2. Inclusion and Exclusion Criteria	13
3.3.3. Interruption or Discontinuation of Treatment.....	15

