3. INVESTIGATIONAL PLAN

3.1. Study Design

This will be a randomized, single-center, controlled, evaluator-blinded, within-subject comparison study of the investigational products (IPs) (CCP-020 [Diacerein 1%] topical ointment and vehicle), and positive and negative controls under occlusive conditions in healthy volunteer subjects. All subjects will have fields designated for the IP patches and the positive and negative control patches at 4 randomly assigned, adjacent sites, for the purpose of determining irritation potential.

The IPs and controls will be applied to one side of the infrascapular area of the back. Evaluation of dermal reactions at the application sites will be assessed clinically using a visual scale that rates the degree of erythema, edema, and other signs of cutaneous irritation (see [Section 3.5.5](#)).

A total of 21 consecutive applications of each product will be made over a study period of 22 days.

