3.4.5. Assignment to Treatment

3.4.5.1. Randomization

Each subject who signs an informed consent form (ICF) will be assigned a screening number. If the subject meets all of the inclusion and none of the exclusion criteria, and successfully completes the screening procedures, they will be enrolled in the study. Upon enrollment, each subject will be assigned a unique subject number and receive a randomization code, indicating application placement of the study materials. Each subject in this study will serve as his or her own control. All subjects will receive the IPs and control products at adjacent application sites.

The IPs (CCP-020 [Diacerein 1%] topical ointment and vehicle) and study controls (SLS and saline) will be assigned in a randomized sequence to test Sites 1 through 4 using a set of independent 4-by-4 Latin squares. The same study material will be applied to the same test site throughout the study.

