3.5. Visit Schedule and Assessments

3.5.1. Study Procedures and Visit Schedule

Screening

At Screening, the subjects will receive any necessary written and verbal information, and the informed consent of each subject will be obtained. Demographic data (including Fitzpatrick skin type) will be recorded, a medical history will be taken, and previous and concomitant medications will be reviewed. Eligibility will be determined by review of the inclusion/exclusion criteria.

- Any written and verbal information
- Informed consent
- Demographics
- Previous/concomitant medication
- Review of inclusion and exclusion criteria
- Medical history (including lifestyle and habits)
- Examination of application site area

Table 1: Fitzpatrick Skin Types

I	Always burns easily, never tans
II	Always burns easily, tans minimally
III	Burns moderately, tans gradually
IV	Burns minimally, always tans well
V	Rarely burns, tans very well
VI	Never burn, deeply pigmented ^{4,5}

Day 1

Prior to randomization, women of childbearing potential will be administered a UPT. If the subject fulfills all of the inclusion and none of the exclusion criteria, he/she will be allowed participation in the study. A Baseline evaluation of the patch sites will be performed prior to application of the patches to ensure that no conditions, markings, or coloration of the skin will interfere with interpretation of the study results. Subjects will receive a unique randomization number, which determines the application scheme of the study materials for that individual subject.

A set of 4 application sites will be prepared in accordance with the randomization scheme on either the left or right side of the infrascapular area of the subject's back. The choice of left or right side will be made by the investigative personnel based on a visual inspection of skin clarity and will be recorded on the CRF to ensure consistent placement of the patches at subsequent visits. The distance between the patches will be approximately 1 cm. The numbering of the test sites will remain the same throughout the study. A surgical marker will be used to draw lines to indicate the 4 site locations for compliance purposes. All patches will be affixed to the test sites on the intact skin of the infrascapular area of the subject's back by the investigative personnel.

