4.6. Safety Evaluation

4.6.1. Cumulative Irritancy

Individual irritancy scores will be displayed in a data listing for all subjects, products, and readings, along with the mean and total of the scores.

Frequency counts of each assigned score at each reading for each product will also be presented. No data imputations are to be made for discontinued subjects or missed evaluations. However, when a patch has been discontinued due to limiting irritation, the last observed score (3) will be carried forward through all subsequent readings ([Table 3](#) and [Table 4](#)).

The primary variable of interest is the mean cumulative irritation score. The total cumulative irritation score for each subject and product will also be calculated as the sum of irritation scores. These parameters will be tested pairwise for product differences using Fisher's protected least significant differences in the context of the 2-way analysis of variance (ANOVA), including main effects of subject and product, without interaction. Pairwise differences will be tested only if the null hypothesis of a common mean score for all products is rejected at the 5% level.

Once the maximum score (combined score of a Response Symbols and Numerical equivalents and an effect on super facial layers of the skin) of a 3 or greater is achieved, the cumulative irritancy score will be calculated as the maximum score of 3 for that individual site for the remainder of the study.

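### Products are balanced over Sites 1–4 by Latin squares, but the planned ANOVA has no site term; adding one costs almost nothing, though the gain is unknown

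*Combined protocol and SAP*

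**What the plan says.** Section 3.4.5.1 (Randomization) says that the two investigational products and the two controls "will be assigned in a randomized sequence to test Sites 1 through 4 using a set of independent 4-by-4 Latin squares". Section 3.1 places them "at 4 randomly assigned, adjacent sites", and Section 3.5.1 (Day 1) adds: "The distance between the patches will be approximately 1 cm".

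Section 4.6.1 (Cumulative Irritancy) then specifies a two-way ANOVA "including main effects of subject and product, without interaction", followed by Fisher's protected LSD: "Pairwise differences will be tested only if the null hypothesis of a common mean score for all products is rejected at the 5% level". The Synopsis (Statistical Methods) also lists only subject and product. No section includes site in the model or explains leaving it out. Section 4.1 promises a fuller SAP before database lock, but its text is not in the documents.

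One feature of the layout matters for the remedy. Under Section 3.5.1 the sites are set up "in accordance with the randomization scheme on either the left or right side of the infrascapular area" of the back, and "The choice of left or right side will be made by the investigative personnel based on a visual inspection of skin clarity". The documents do not say whether the four sites form a row or a column, or how they are numbered on each side.

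**The concern.** The randomisation treats position as a blocking factor and the analysis ignores it. With Latin-square balance, a site effect common to all subjects cancels out of the product means, so the true precision of a product comparison is unaffected. Without a site term, the same effect is counted in the residual mean square. The standard errors are then larger than the data warrant, and both the overall F test and the pairwise tests reject too seldom.

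The primary objective is to find out whether CCP-020 irritates skin, so a conservative test errs towards missing irritation. Section 4.2 gives no power calculation, so there is no documented margin to absorb a loss.

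**Working it through.** **Inputs.** Section 4.2 gives 30 evaluable subjects; with four sites each, that is 120 subject-by-site scores. The overall F test is at 5% (Section 4.6.1). The level and sidedness of the pairwise tests are not stated; two-sided 5% is assumed. The documents give no residual variance, site variance or target difference, so these are assumptions shown over a range. The sample size rests on convention alone, so there is no power figure to reproduce.

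**Cost of the term.** Error df without site: 120 − 1 − 29 − 3 = 87. With site: 87 − 3 = 84. The critical t moves from 1.9876 to 1.9886 and the critical F from 2.709 to 2.713. Because 30 is not a multiple of 4 (seven full squares plus two rows), adjusting for site raises the variance of a product contrast by 0.1–0.2%. With no site effect, simulated power is 81.1% without site and 81.0% with it.

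**Inflation if site is left out.** Let v be the mean squared site deviation (divisor 4) divided by the residual variance σ². A site effect shared by all subjects adds 30 × 4v × σ² = 120vσ² to the error sum of squares, so

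E[MSE without site] = σ² × (1 + 120v/87),

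and the standard error is too wide by the square root of the bracket. For a linear gradient with step d, v = 1.25d²/σ², so Sites 1 and 4 differ by 3√(v/1.25) residual SDs.

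| v | Site 1 to 4 gap (SD) | 1 + 120v/87 | SE ratio |
|---|---|---|---|
| 0.02 | 0.38 | 1.028 | 1.014 |
| 0.05 | 0.60 | 1.069 | 1.034 |
| 0.10 | 0.85 | 1.138 | 1.067 |
| 0.25 | 1.34 | 1.345 | 1.160 |
| 0.50 | 1.90 | 1.690 | 1.300 |

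**Power, CCP-020 versus vehicle.** Simulation assumptions: true difference 0.75 residual SD, SLS at +2 SD, normal errors, linear gradient, random Latin squares cut to 30 subjects, F test applied first, 4,000 trials per case (Monte Carlo SE up to 0.8 points). Entries are % power without / with site.

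| v | Same gradient in all | Reversed in a quarter | Reversed in half |
|---|---|---|---|
| 0.02 | 80 / 81 | 81 / 81 | 81.3 / 81.1 |
| 0.05 | 80 / 82 | 80 / 81 | 79.3 / 79.1 |
| 0.10 | 78 / 81 | 77 / 78 | 76.7 / 76.5 |
| 0.25 | 73 / 82 | 70 / 72 | 69.6 / 69.2 |
| 0.50 | 62 / 82 | 61 / 65 | 59.5 / 58.8 |

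The mean estimated difference was 0.745–0.755 in every case, so there is no bias. When the gradient reverses in half the subjects, the term recovers nothing.

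**False positives, same setting, no true CCP-020 versus vehicle difference.** At v = 0, 0.10, 0.25 and 0.50 with a common gradient, the rejection rate is 5.1, 4.1, 2.5 and 1.1% without site and 5.0, 5.2, 5.4 and 4.6% with it. With the gradient reversed in half, the rate without site is 5.0, 4.9, 5.2 and 5.5%. The conservatism due to site therefore arises only from a site effect that subjects share.

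**Capped scores.** The endpoint averages daily scores of 0–3, with 3 carried forward. Under an assumed latent model (21 readings, about half the non-SLS sites near zero, 1,500 trials), the SE ratios at v = 0.05, 0.10, 0.25 and 0.50 are 1.018, 1.036, 1.086 and 1.158. The excess is about half that of the continuous case.

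**The case against.** The strongest reply is that this is an optional refinement. The subject-plus-product model is valid, and nothing is lost if the sites respond alike. The striking loss (62 versus 82%) needs Sites 1 and 4 to differ by 1.9 residual SD. With 2 cm pads and 1 cm gaps, four sites in a row span only 4 × 2 + 3 × 1 = 11 cm, and nothing in the documents suggests a gradient that steep. This stands: the low end is the more likely, and the gain there is 1 to 3 points.

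Capped scores weaken the case further. In the capped model, with 800 trials per case, power for CCP-020 versus vehicle is 58.1 versus 59.1% at v = 0.02, 57.1 versus 58.9% at v = 0.05, and 54.4 versus 58.2% at v = 0.10. With milder products the SE ratios at those values fall to 1.003, 1.012 and 1.025. When CCP-020, vehicle and saline respond alike, the CCP-020 versus vehicle test rejects in about 2–3% of trials, or fewer when scores sit nearer zero, with or without the site term. Pooling SLS and near-zero products into one error variance explains most of that. This also stands: the return to about 5% shown above holds only for normal errors of equal variance.

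Section 4.1 puts the focus on comparisons with the controls. In the capped model, CCP-020 versus SLS has 100% power either way, and CCP-020 versus saline moves only from 72.8 to 73.0% at v = 0.02. Section 4.6.1, however, tests all product pairs, and the error term is common to them.

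Finally, the SAP may add the term. That is possible, but the protocol states a specific model without it, so the change has to be asked for.

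**Conclusion.** The point holds as a matter of efficiency, not validity. The size of the loss cannot be fixed from the documents. If a common site effect exists it is probably small, with standard errors a few per cent too wide and a point or so to three points of power; it would be substantial only under a steep gradient shared by all subjects. These figures rest on assumed values of v, a 0.75 SD difference and, for the main power table, normal errors. The term recovers only what subjects share: a subject-specific site difference, or a gradient that flips with the side of the back, stays in the error either way. The change should still be made, because it uses a factor the trial already randomises by and its price is negligible even if it gains nothing.

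**What to change.** In Section 4.6.1, the Synopsis and the SAP, specify an ANOVA with subject, product and test site (1–4, as randomised). Run the overall product F test in that model and take pairwise differences from site-adjusted least-squares means.

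In Section 3.5.1, state the site layout and how Sites 1–4 are numbered on the left and right sides, so that one number always means one position. Otherwise the term may recover little.

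The cost is one model term and a sentence on numbering. Letting the site effect differ by side would recover a reversed gradient (power 69 to 80% at v = 0.25 with half reversed). It uses 6 of 87 df and widens standard errors by about 2% when there is no site effect, so it is not proposed as the default.

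Separately, Section 3.3.3 provides for moving a patch after a reaction, whereas Section 3.4.5.1 keeps each material on one site throughout. These must be reconciled. Site as randomised keeps the model defined in the meantime, although readings after a move would come from another location.

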4.6.2. Adverse Events

Adverse events will be summarized as an overall incidence of at least one event, incidence within body systems only, incidence by body system and preferred term, and by highest severity. Each subject will contribute only once (e.g., the first occurrence) to each of the rates, regardless of the number of occurrences (events) the subject experiences.

Treatment-emergent AEs will be summarized and tabulated by the system organ class and preferred term, by severity (mild, moderate, severe) and by relationship to study product (Yes or No).

Treatment-emergent will be defined as any AE with an onset date on or after the first study product administration date. Any event with a missing onset date will be included as a treatment-emergent AE.

Deaths and SAEs will be listed by subject.

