3.4.5.2. Blinding

The treatments (IPs and control) will not be blinded to investigative personnel involved in the preparation/application and removal of treatments.

Investigative personnel who are involved in the preparation/application and removal of the treatments will not perform the evaluation of skin responses. Investigative personnel who are involved in the preparation/application and removal of the treatments will be unblinded. The trained evaluator who will be evaluating skin responses will be blinded to IPs and control and the

treatment allocation; however, because of the demarcations/skin coloration remaining on the skin following patch removal, complete blinding of the evaluators cannot be completely assured.

Investigative personnel, including the Investigator and trained evaluator involved in the evaluation of responses, will remain blinded during the course of the study until Database Lock and finalization of the Statistical Analysis Plan (SAP).

In the event of an emergency, if possible, the Investigator or designee will contact the Sponsor with notification of the intent to unblind the treatment codes prior to the actual unblinding. If it is not possible to notify the Sponsor prior to the unblinding, the Investigator or designee will contact the Sponsor immediately following the unblinding procedure and follow with a written notification to document the exact manner in which the code was broken and the justification for the unblinding. The Investigator will communicate the treatment identification to only the investigative personnel who require the information to manage the emergency. Unblinding will happen on site at TKL.

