CCP-020 (Diacerein 1%) topical ointment and vehicle will be applied in the amount of 0.2 mL to a 2 cm x 2 cm Webril® patch pad via Eppendorf® Combitips and then applied to the subject's skin surface as soon as possible following product application. The sterile 0.9% saline (negative control) and 0.2% SLS (positive control) will be applied to a 2 cm x 2 cm Webril® patch pad via pipette and then applied to the subject's skin surface. All 4 products will be evaluated under occlusive patch conditions by means of application to a 2 cm x 2 cm Webril® pad. The patches will be secured with hypoallergenic tape as needed.

Days 2-21

The patches will be removed 24 ± 4 hours after application. Excess study material will be removed with a tissue to avoid the transference of materials between sites by investigative personnel. Investigative personnel responsible for patch application/removal will wipe each site with distilled water. A trained and blinded evaluator will perform an assessment of all test sites for irritation symptoms immediately (within 30 minutes) following patch removal using the scoring system detailed in [Section 3.5.5](#). Scores will be entered into the data sheets by the evaluator. If the skin is not disrupted (skin irritation score ≤ 2), identical treatments and patches will be re-applied to the same test sites with investigational products and control solutions using the procedures above. Separate individuals will be responsible for evaluation of the test sites (blinded) and patch application/removal (unblinded). Individual patches may be discontinued if a reaction of a grade of 3 or greater (see [Section 3.5.5](#)) occurs at any point during the study. Further patch applications of that product on that individual subject will be terminated. A NP symbol and a score of 3 will be assigned for all subsequent days.

The procedure for removal of study materials, evaluation of test sites, and application of fresh study materials will be repeated for 20 consecutive days, for a total of 21 applications per product per subject. A total of 21 post-baseline evaluation scores will be assigned to assess cumulative irritancy.

A new tube of CCP-020 [Diacerein 1%] topical ointment and vehicle will be opened every 14 days due to qualified suitability (see [Section 3.4.2](#)).

In addition, at each of the study visits, concomitant medications and AEs will be reviewed and recorded.

Day 22 (End of Study)

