3.6.2.4. Relationship of Adverse Events to Study Treatments

The Investigator is to classify the drug relationship of an AE according to the definitions outlined in [Table 6](#).

Table 6: Relationship of AE to Study Drug

Association	Definition
Not related	(1) the existence of a clear alternative explanation (e.g., mechanical bleeding at surgical site) or (2) non-plausibility, e.g., the subject is struck by an automobile or cancer developing a few days after drug administration.
Unlikely	There is no medical evidence to suggest that the AE may be related to study drug usage, or there is another more probable medical explanation.
Possible	There is medical evidence to suggest that there is a reasonable possibility that the AE may be related to study drug usage. However, other medical explanations cannot be excluded as a possible cause.
Probable	There is strong medical evidence to suggest that the AE is related to study drug usage.
Definite	A clinical event, including laboratory test abnormality (if applicable), in which there is no uncertainty in its relationship to test drug (e.g., positive Rechallenge).

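### The planned adverse event tables cannot give CCP-020's own rate of local adverse events that fall outside the irritation scales

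*Combined protocol and SAP*

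**What the plan says.** **Exposure.** Section 3.4.5.1: "All subjects will receive the IPs and control products at adjacent application sites". The four materials go to Sites 1 to 4 by Latin squares, and each keeps its site throughout.

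**Who rates relationship.** Section 3.6.2.4: "The Investigator is to classify the drug relationship of an AE", on the five categories of Table 6. The blinding rule in section 3.4.5.2 covers the same person: "including the Investigator and trained evaluator involved in the evaluation of responses, will remain blinded during the course of the study". That blind is lifted only at database lock, once the SAP is final.

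**What is recorded for an AE.** Section 3.6.2.1 lists duration, severity, relationship, action taken and outcome. Test site is not listed.

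**What is tabulated.** Section 4.6.2 gives incidence overall, by body system, by preferred term and by severity, and also "by relationship to study product (Yes or No". It adds: "Each subject will contribute only once (e.g., the first occurrence) to each of the rates". It names neither product nor site as a dimension of these tables.

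**What is not an AE.** Sections 3.6.1, 3.6.2.1 and 3.6.6 exclude any response that Tables 3 and 4 can denote. Those responses are scored, and section 4.6.1 lists the scores and counts their frequencies for each product.

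**The concern.** AE evaluation is the additional safety assessment in section 2, and the synopsis covers local as well as systemic events. For a local event, the useful question is which of the four patches it occurred under. One of the four is a deliberate irritant and another is the test product. A per-subject table with one Yes/No answer mixes them.

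The mixing works in both directions. An itch under the SLS patch can add to a rate that readers take as describing CCP-020. Conversely, because each subject counts once per rate, a subject who itches first under SLS and later under CCP-020 adds only one count, and the CCP-020 event adds nothing visible.

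The design itself contains the information needed to separate them. The site number and the randomization code link a local event to the product under that patch. The AE section does not ask for the site.

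**Working it through.** There is no planned figure to reproduce. Section 4.2 justifies 30 evaluable subjects by convention, and the documents give no AE rate. The check sets the sections side by side, then uses arithmetic to show what a pooled count can and cannot reveal.

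**1. What does the relationship rating refer to?** Three terms are used: *investigational patch* (synopsis), *study drug* (3.6.2.1 and 3.6.2.4) and *study product* (4.6.2). None is defined as including or excluding the controls. Section 3.5.1 uses the broad sense: "All 4 products will be evaluated under occlusive patch conditions". Section 3.4.5.1 keeps the groups apart: "The IPs (CCP-020 [Diacerein 1%] topical ointment and vehicle) and study controls (SLS and saline) will be assigned in a randomized sequence". Either reading is possible. Under the narrow one, a blinded rater would not know which sites hold the investigational products.

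**2. Which local events can enter the AE tables?** Tables 3 and 4 cover erythema, edema, papules, vesicles, spreading, glazing, peeling, fissures, exudate and erosions. All of these are excluded from AEs. Burning or stinging (B) and itching (I) are in Table 5, which the exclusion does not name. They carry no numerical score, so the score counts in 4.6.1 do not cover them, and no summary of them is planned. The protocol does not say whether a B or I notation also generates an AE record.

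**3. What does a pooled count say about CCP-020?** Suppose k of N treated subjects have a given local AE. CCP-020's own count lies between 0 and k, and nothing in 4.6.2 narrows that. For k = 6 and N = 30, the range is 0/30 = 0% to 6/30 = 20%. Section 4.3 counts all treated subjects, and section 3.3.1 enrols enough to give 30 completers, so N may exceed 30. With N = 36 (assumed), the upper end is 6/36 = 16.7%.

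**4. Can different situations give the same table?** Yes. All rates here are assumptions: vehicle 2%, saline 1%, and sites independent. The pooled rate is 1 − ∏(1 − pᵢ).

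| CCP-020 | SLS | Calculation | Pooled rate |
|---|---|---|---|
| 5% | 10% | 1 − 0.95 × 0.98 × 0.99 × 0.90 | 17.05% |
| 10% | 5% | 1 − 0.90 × 0.98 × 0.99 × 0.95 | 17.05% |
| 0% | 20% | 1 − 1.00 × 0.98 × 0.99 × 0.80 | 22.4% |
| 10% | 10% | 1 − 0.90 × 0.98 × 0.99 × 0.90 | 21.4% |

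The first two rows are identical. The last two differ by 1.0 point, or about 0.3 of a subject in 30 (6.7 against 6.4 expected), although CCP-020's true rate is 0% in one and 10% in the other.

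**5. What would a by-product table show?** With 30 subjects, 0/30 has an exact 95% interval of 0 to 11.6%, and 3/30 has 2.1% to 26.5%. These are imprecise, but they describe CCP-020.

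**The case against.** The strongest reply is that most of the problem has been designed out. The visible reactions expected from an irritant are scored on Tables 3 and 4, kept out of the AE tables, and reported and compared by product under 4.6.1. This stands, and it limits the point to local events outside those tables.

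A reader might infer that SLS reactions in general will inflate the related-AE rate. The exclusion rule rules that out for scorable reactions. A reader might also infer that an SLS-site event is bound to count as related to study product. The documents do not settle this, because the term is undefined. Section 5.7 uses it for supplies returned as the sponsor designates, which favours the narrower sense.

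Three further replies stand in part:

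- B and I are recorded with, or in place of, a site's score. They can be mapped to product after unblinding, so the information is not lost, but no summary of it is planned.
- The synopsis's *investigational patch* could be read as patch-level attribution. Neither 3.6.2.1 nor 4.6.2 carries this through.
- Section 4.1 promises a fuller SAP, and section 5.6.1 says the case report forms identify the product being evaluated. Neither states that an AE will carry its site. A SAP can add a table, but it cannot reliably recover a field that was never required.

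Blinded rating is not a fault, since it protects the rating from knowledge of the product. Systemic AEs cannot be assigned to one product when all four are worn together, whatever the tables look like.

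**Conclusion.** The point holds in limited form. The AE tables described in 4.6.2 give no local AE rate for CCP-020, because all four products are worn at once, no test site is required for an AE, the rater is blinded, and the relationship target is undefined. The gap covers local events outside Tables 3 and 4, chiefly burning, stinging and itching. It does not touch the primary irritation analysis.

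Its size cannot be stated, because the documents give no AE rate. The 0-to-k range needs no assumption about rates. The percentages in the working are illustrations resting on assumed counts, rates and denominators, with independent sites assumed for the pooled rates.

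It would be too strong to say that CCP-020's local tolerability cannot be read at all. The irritation scores are reported by product, and the B and I notations could be. This is a low-cost improvement to the safety reporting and does not threaten the trial's main conclusion.

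**What to change.** 1. Add the test site (1 to 4, or non-local) to the AE descriptors in 3.6.2.1 and to the case report form.
2. Have the Investigator rate relationship of local AEs by site, while still blinded.
3. After unblinding, tabulate application-site AEs and the B and I notations by product, counting each subject once per product. State whether a B or I notation is also recorded as an AE.
4. Use one defined term for the relationship target in the synopsis, 3.6.2.1, 3.6.2.4 and 4.6.2, say whether it includes SLS and saline, and say which Table 6 categories count as Yes.
5. Keep the pooled relationship table for systemic AEs, with a note that the design cannot attribute them to one product.

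The cost is one case report form field and a slightly longer AE output. Attribution by site will not be perfect, since patches are about 1 cm apart and reactions can spread, but the S notation can flag those cases.
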